## LIST OF ABBREVIATIONS

ABCD	Amphotericin B colloidal dispersion
ABLC	Amphotericin B lipid complex
AmBd	Amphotericin B deoxycholate or conventional amphotericin
AE	Adverse event
AIDS	Acquired immunodeficiency syndrome
ALT	Alanine transaminase
AST	Aspartate transaminase
ART	Antiretroviral therapy
C-AMB	conventional amphotericin B
CD 4 count	CD 4 + T-lymphocyte count
CD	Cluster of Differentiation
CNS	Central Nervous System
CM	Cryptococcal meningitis
CSF	Cerebrospinal Fluid
DAIDS	Division of AIDS
HGB	Hemoglobin
HIV	Human immunodeficiency virus
ICP	Intracranial Pressure
IV	Intravenous
L-AMB	Liposomal amphotericin B
NAP	National AIDS Programme
NRS	Numerical rating scale
OD	Once a day
OI	Opportunistic infection
PLT	Platelet
PLHIV	People living with HIV
RCT	Randomized control trial
SD	Standard deviation
SGPT	Serum Glutamic Pyruvic Transaminase
SGOT	Serum Glutamic Oxaloacetic Transaminase

## **LIST OF ABBREVIATIONS**

UNAIDS	Joint United Nations Programme on HIV/AIDS
WBC	White blood cells
WHO	World Health Organization

# 1. INTRODUCTION

## 1.1. Background Information

According to data of Joint United Nations Program on HIV/AIDS (UNAIDS, 2019), a population of 37.9 million of globally was living with HIV, and the annual number of deaths due to AIDS-related illnesses was 770,000 worldwide. Among them, 5.9 million people were from Asia and the Pacific region, with the estimated 200,000 AIDS-related deaths. In 2018, Myanmar had 240,000 adults and children living with HIV and there were about 7800 AIDS-related deaths (UNAIDS, 2019a). Although UNAIDS figured Myanmar high on its list of priorities as one of the six countries in Asia for the Global Fast Track Strategy to end HIV in 2030, there were still 11,000 adults and children newly infected with HIV in 2018 (UNAIDS, 2019b).

AIDS stands for acquired immune deficiency syndrome that develops as a result of advanced HIV infection which has destroyed the immune system and thus the body loses the ability to fight the organisms that cause diseases. The organisms take advantage of a weakened immune system, causing severe life-threatening opportunistic infections (OIs) (AIDSinfo, 2019b) that include *Pneumocystis pneumonia* (PCP), *toxoplasma encephalitis*, *cytomegalovirus* (CMV) retinitis, *cryptococcal meningitis*, *tuberculosis*, *disseminated Mycobacterium avium complex* (MAC) disease, and *pneumococcal respiratory disease* (AIDSinfo, 2019a).

*Cryptococcal meningitis* (CM) is the most common opportunistic fungal infection of the central nervous system (CNS) caused mostly by *Cryptococcus neoformans*. For people who have been exposed, the fungus remains largely latent in the body and most will never fall ill. But for those living with a compromised immune system, infection can spread from the lungs to the brain and spinal cord, causing meningitis (Rajasingham et al., 2017). It usually occurs in patients with advanced immunosuppression at CD4 count  $< 100/\text{mm}^3$  (National AIDS Programme, 2017) and a major cause of morbidity and mortality especially in the developing world (WHO, 2019), with mortality within the first 3 months of diagnosis (Hevey et al., 2019). There were an estimated 220,000 cases of CM that occur among people with HIV/ AIDS worldwide each year, resulting in nearly 181,000 death (Rajasingham et al., 2017) and the disease account for 15% of AIDS-related deaths (Ponatshego et al., 2019).

Patients may present with headaches, fever, meningism, features of raised intracranial pressure, seizures (Heckmann & Bhigjee, 2014). In African and Vietnam trial, headache (100 %) was the most prominent clinical presentation which was followed by fever (77%), neck stiffness (73%), abnormal mental status (46.7%) and seizure (19.2%) (Day et al., 2013 & Molloy et al., 2018).

In WHO guideline (2018) for the management of cryptococcal disease, the preferred regimen is a short-course (one-week) induction regimen with amphotericin B deoxycholate and flucytosine followed by 1 week of fluconazole. It has been estimated that inductive treatment of Cryptococcal meningitis with flucytosine alone causes a prohibitive expense for low GDP nations (Shiri, 2019) and due to this reason, it is unavailable in all low and middle-income countries (Loyse et al., 2013). Thus, the treatment of cryptococcal meningitis in resource-limited settings is challenging (Molloy et al., 2018) and alternative options of two weeks amphotericin B deoxycholate plus fluconazole are used depending on drug availability (WHO, 2018). According to guidelines for clinical management of cryptococcosis in Myanmar, initiation of treatment is with Amphotericin plus Fluconazole for at least 2 weeks followed by consolidation with Fluconazole for 8 weeks followed by maintenance of Fluconazole until CD4 count rises to 200/mm^3 with ART (National AIDS Programme, 2017).

As a partner drug with amphotericin B, flucytosine was superior to fluconazole in cryptococcal meningitis in patients with HIV infection as one week of amphotericin B plus flucytosine was associated with the lowest mortality of 24.2% in ACTA (Advancing cryptococcal meningitis treatment for Africa) trial (Molloy et al., 2018). Moreover, clearance of cryptococci from the cerebrospinal fluid (CSF) was exponential and significantly faster with amphotericin B plus flucytosine than, amphotericin B plus fluconazole (Day et al., 2013).

Even where flucytosine (5FC) is available, it is often not administered because of overstated fears regarding toxicity (Loyse et al., 2013). The most serious drug-related adverse effect of 5FC is bone marrow suppression and hepatotoxicity (Vermes et al., 2000). In California's study, 5FC had been discontinued in over half of the patients because of cytopenia (Chuck & Sande, 1989). One patient in South Africa study also was discontinued 5FC because of thrombocytopenia on day-4 and the regimen was switched early to fluconazole (Bicanic et al., 2008). And also grade-4 neutropenia was recorded in 3.2% of the patients with 5FC (Molloy et al., 2018). But

in Thailand study, the treatment was well tolerated and there was no severe bone-marrow depression with 5FC (Brouwer et al., 2004).

Regarding amphotericin B Deoxycholate, its major drug-related adverse effects include nephrotoxicity and anemia (Bicanic et al., 2015). In Vietnam trial, Grade 3 and 4 anaemia were most prominent between amphotericin B plus flucytosine (35%) and amphotericin B plus fluconazole group (29%) (Day et al., 2013). Renal impairment occurs in nearly all patients treated with clinically significant doses of amphotericin. Fluconazole is relatively nontoxic, but reported to cause abnormalities in liver enzymes and very rarely, clinical hepatitis (Lampiris & Maddox, 2018).

Although WHO treatment guidelines recommend treatment regimen containing flucytosine as the preferred therapy, in clinical practice, treatment is highly variable due to drug costs, availability, and ability to monitor and manage drug-related toxicities (Perfect, 2010). A previous study was carried out in Mandalay for cryptococcal meningitis with fluconazole monotherapy by Than-Maung in 2006 and amphotericin B monotherapy by Myo-Thet-Naing in 2013 but the effectiveness and safety of amphotericin with flucytosine and fluconazole combination regime have not been studied in Myanmar. Thus, this study will provide information regarding the clinical effectiveness and safety of this treatment regimen for management of HIV-associated cryptococcal meningitis in Myanmar.

## **1.2. Justification**

Cryptococcal meningitis is an AIDS-defining illness mostly caused by the fungus, *Cryptococcus neoformans*. In high-income countries, the use of amphotericin B in combination with a more expensive drug, flucytosine, is most effective for the management of cryptococcal meningitis; but access to flucytosine is severely limited in middle and low-income countries. In Myanmar, currently recommended regimen for cryptococcal meningitis are combination of amphotericin B with fluconazole. Although amphotericin plus flucytosine followed by fluconazole therapy is the currently preferred regimen in WHO treatment guidelines, it is not still commonly used in Myanmar clinical practice because of its limited availability. Therefore, the data regarding tolerability and clinical effectiveness of flucytosine are unavailable for Myanmar patients.

Although trials were carried out for investigating the effectiveness of flucytosine in the HIV population of Africa, the variability in drug response can occur

in Myanmar patients due to the racial and genetic differences and whether it is effective and safe for Myanmar people is a great curiosity question for clinicians and healthcare workers. In Myanmar, amphotericin plus flucytosine followed by fluconazole regimen will be supplied by National AIDS Program (NAP) and indicated in 2020. Thus, the documents for effectiveness and safety profile need to be established. This is the reason that the effectiveness and safety of amphotericin B with flucytosine and fluconazole combination therapy should be studied. From this study, it can provide information to physicians regarding the effectiveness as well as safety of those drugs in the management of cryptococcal meningitis in HIV patients.

## 2. LITERATURE REVIEW

### 2.1. Cryptococcosis

#### 2.1.1. History

Cryptococcosis is an important cosmopolitan, infectious, mycotic disease of man and animals caused by the yeast, *Cryptococcus neoformans* which exists as saprobe in the environment. The disease is also known as Busse Buschke's disease, European blastomycosis or Torulosis. The disease was considered as sleeping disease in older days became an awakening giant in present era. Over a period of more than one hundred years ago, in 1894 *Cryptococcus neoformans* was discovered when this yeast was isolated independently from peach juice in Italy, by Sanfelice and from the tibial lesion of a patient in Germany by Busse (1894) and Buschke (1895), simultaneously. Sanfelice studied the pathogenicity of organisms in laboratory animals and gave name as *Saccharomyces neoformans* to the pathogen (cited by Nayak et al., 2010). In 1901, Jean-Paul Vuillemin, (Barnett, 2010) at Nancy University in France, named Busse's yeast *Cryptococcus hominis* and renamed Sanfelice's yeast *Cryptococcus neoformans* because neither yeast formed ascospores, as would be expected of a member of the genus *Saccharomyces*.

#### 2.1.2. Epidemiology

*Cryptococcus neoformans* and *Cryptococcus gattii* are environmental, basidiomycetous yeasts. Unlike other pathogenic fungi, these yeast cells possess large polysaccharide capsules. Bird droppings (particularly pigeon droppings) enrich for the growth of *Cryptococcus neoformans* and serve as a reservoir of infection. The organism grows luxuriantly in pigeon excreta, but the birds are not infected. It is estimated that 1g of dry pigeon excreta may contain up to 50 million viable cells of *C. neoformans*.

It is isolated readily from dry pigeon feces, as well as trees, soil, and other sites. *Cryptococcus gattii* is less common and typically associated with trees in tropical areas. Both species cause cryptococcosis, which follows inhalation of desiccated yeast cells or possibly the smaller basidiospores (Brooks et al., 2013). It can infect any organ in the body organs (e.g. skin, eyes, prostate), but has a predilection for the lung and the CNS. The lung is the usual portal of entry and symptoms range from

asymptomatic colonization to severe pneumonia. Meningitis is the most frequent manifestation of cryptococcosis (AIDSinfo, 2019a).

[figure not shown]

Figure (1) Natural history of cryptococcosis (Brooks et al., 2013)

*Cryptococcus neoformans* occurs in immunocompetent persons but more often in patients with HIV/AIDS, hematogenous malignancies, and other immunosuppressive conditions. In HIV-infected patients, the disease is associated with profound immunosuppression, usually occurring at CD4 counts <100 cells/ $\mu$ l. There is a greater likelihood of involvement outside the CNS and relapse if antifungal therapy is discontinued prior to effective antiretroviral therapy (AIDSinfo, 2019a).

Overall, approximately one million new cases of cryptococcosis occur annually, and the mortality approaches 50%. More than 90% of these infections are caused by *C. neoformans*. In sub-Saharan Africa, the epicenter of HIV/AIDS, *Cryptococcus neoformans* is the leading cause of meningitis with an estimated one million new cases and 600,000 deaths per year (Brooks et al., 2013).

### **2.1.3. Morphology and identification**

In culture, *Cryptococcus* species produce whitish mucoid colonies within 2–3 days. Microscopically, in culture or clinical material, the spherical budding yeast cells (5–10  $\mu\text{m}$  in diameter) are surrounded by a thick non-staining capsule. All species of *Cryptococcus*, including several nonpathogenic species, are encapsulated and possess urease. However, *C. neoformans* and *C. gattii* differ from nonpathogenic species by the abilities to grow at 37°C and the production of laccase, a phenol oxidase, which catalyzes the formation of melanin from appropriate phenolic substrates (eg, catecholamines). Both the capsule and laccase are well characterized virulence factors (Brooks et al., 2013).

There are four serotypes based on the capsular polysaccharide, glucuronoxylosemannan (GXM) (Klatt, 2019). Capsular types A through D correspond to the variants *C. neoformans* var. *grubii* (A), *C. neoformans* var. *gattii* (B and C) and *C. neoformans* var. *neoformans* (D) (Warkentien, T & Crum-Cianflone, NF., 2010).

### **2.1.4. Pathogenesis**

*Cryptococcus* is a basidiomycetous yeast that exists in the environment in the sexual form and produces hyphae with terminal basidiospores (chains of unbudded yeast) (Klatt, 2019). To enter the alveolar spaces of the lungs and establish pulmonary infection, an organism must produce viable forms smaller than 4  $\mu\text{m}$  in diameter. The typical vegetative form of *C. neoformans* is the yeast form with a cell diameter of 2.5 to 10  $\mu\text{m}$  (Nayak et al., 2010). When the 3 $\mu\text{L}$  basidiospores break off they become aerosolized and may be inhaled into the alveoli. Less commonly, the portal of entry is the gastrointestinal tract or the skin (Klatt, 2019). The organism remains dormant in the lungs until the immune system weakens and then reactivates and disseminate to the central nervous system, other body sites such as the skin, bone, joint, eye, heart, adrenals and prostate gland. (Nayak et al., 2010, Brooks et al., 2013). The inflammatory reaction is usually minimal or granulomatous (Brooks et al., 2013)

*Cryptococcus* may survive within human because of a polysaccharide capsule that allows it to evade phagocytosis. Capsular polysaccharides include galactoxylomannan as well as glucuronoxylosemannan, and they impart resistance to phagocytosis. In addition, a phenol oxidase enzyme uses catecholamines as substrate to produce melanin, which accumulates in the cell wall, and synthesis of catecholamines

for neurotransmitters may predispose to involvement of the central nervous system (Klatt, 2019).

### **2.1.5. Clinical presentation**

In HIV-infected patients, cryptococcosis commonly presents as a subacute meningitis or meningoencephalitis with fever, malaise, and headache. Classic meningeal symptoms and signs, such as neck stiffness and photophobia, occur in only one-quarter to one-third of patients. Some patients experience encephalopathic symptoms, such as lethargy, altered mentation, personality changes, and memory loss that are usually a result of increased intracranial pressure (AIDSinfo, 2019a). In African trial, headache (98.2 %) was the most prominent presentation which was followed by fever (52.9%), abnormal mental status (46.7%) and seizure (19.2%) (Molloy et al., 2018).

The findings in this study are comparable with those from studies from Myanmar. In the studies of Myo-Thet-Naing and Nyein-Chan-Win, headache was the most common presentation (100%). Other clinical parameters in order of decreasing frequency on admission were fever (58.70%), neck stiffness (45.65%) and impaired conscious level (13.04%) (Myo Thet Naing, 2013). In the study of Than-Maung, the most common clinical features are headache (97.87%), fever (85.11%), neck stiffness (63.83%), abnormal mental status (42.55%), convulsion (41.3%), focal neurological symptoms (14.89%) and papilledema (12.77%).

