#### **4.7. Sample Size Determination and Sampling Procedure**

##### **4.7.1. Sample Size Determination**

The sample size was calculated by using the following formula

$$z_{(1-\frac{\alpha}{2})}^2 p (1-p)$$

$$n = \frac{z_{(1-\frac{\alpha}{2})}^2 p (1-p)}{d^2}$$

Sample size for clinical safety,

Where,

p = Proportion of absence of grade III/IV anaemia in patients with HIV-associated cryptococcal meningitis infection after being treated with Amphotericin B, Flucytosine plus Fluconazole  
= 0.83 (Molloy et al., 2018)

z = Standard normal deviate = 1.96 (95% CI)

d = Absolute precision = 0.14

n = minimal required sample size = 27

Sample size for clinical effectiveness,

Where,

p = Proportion of improvement of headache in patients with HIV-associated cryptococcal meningitis infection after being treated with Amphotericin, Flucytosine plus Fluconazole  
= 0.8

z = Standard normal deviate = 1.96 (95% CI)

d = Absolute precision = 0.15

n = minimal required sample size = 27

So, the required sample size is 27.

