#### **4.7.2 Sampling Method**

All patients admitted to the inpatient departments of SHW, SHM and SHT during the study period will be included.

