#### **4.9. Data Management and Analysis**

Data will be collected by using pre-constructed pro forma. Following data collection and prior to data entry, all data will be carefully screened for accuracy.

Data entry will be done by using Microsoft Excel 2019. The data will be statistically analyzed by using computerized statistical software SPSS (Statistical Package for Social Science Version 21).

Data summarization for description will be done by showing frequency distribution tables and appropriate graphs. The parameters for clinical effectiveness and laboratory-defined adverse event gradings will be described by number, percentage in treatment group.

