#### 4.12. Algorithm

## 5. DUMMY TABLES

Table 4. Number of Cryptococcal meningitis in patients with HIV infection enrolled from individual specialist hospital

Hospital	Number (N)	Percentage (%)
Specialist hospital Waibargi		
Specialist hospital Mingalardon		
Specialist hospital Thakeyta		
Total		

Table 5. Distribution of age among study group of Cryptococcal meningitis in patients with HIV infection

Age (completed years)	Amphotericin B, Flucytosine plus Fluconazole group	
	Number	Percentage
≤20		
21-40		
>40		
Total		

Table 6. Distribution of gender among study group of Cryptococcal meningitis in patients with HIV infection

Gender	Amphotericin B, Flucytosine plus Fluconazole group	
	Number	Percentage
Male		
Female		
Total		

Table 7. Frequency distribution of headache among study group by Numerical rating Scale at day-1, day-7 and day-14

Days	Headache	Amphotericin B, Flucytosine plus Fluconazole group	
		Number	Percentage
day-1	No pain		
	Mild		
	Moderate		
	Severe		
	Intolerable		
Day-7	No pain		
	Mild		
	Moderate		
	Severe		
	Intolerable		
Day-14	No pain		
	Mild		
	Moderate		
	Severe		
	Intolerable		

Table 8. Clinical effectiveness of study group by assessing presence of headache, fever, convulsion, abnormal mental status and death at day-1, day-7 and day-14

Clinical parameters	Amphotericin B, Flucytosine plus Fluconazole group					
	Day 1		Day 7		Day 14	
	N	%	N	%	N	%
Headache						
Fever						
Convulsion						
Abnormal mental status						
Death						

Table 9. Laboratory-defined adverse events of amphotericin B, flucytosine and fluconazole at baseline and day-7 and day-14 by DAIDS grading

Days	DAIDS Grading	Hematological parameters & Biochemical parameters								Total
		Anaemia N (%)	Neutropenia N (%)	Thrombocytopenia N (%)	Elevated ALT level N (%)	Elevated AST level N (%)	Hypokalemia N (%)	Hyper creatinemia N (%)		
Baseline	Grade 1									
	Grade 2									
	Grade 3									
	Grade 4									
Day-7	Grade 1									
	Grade 2									
	Grade 3									
	Grade 4									
Day-14	Grade 1									
	Grade 2									
	Grade 3									
	Grade 4									

Table 10. Proportion of patients with grade 3 and 4 adverse events of hematological parameters at baseline, day-7 and day-14

	Grade 3 and 4 adverse events	Baseline		Day -7		Day -14	

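### Table 8 shows only the net change in each symptom's prevalence; it should also be split by day-1 status so that resolution, new onset and death can be told apart

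*Combined protocol and SAP*

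**What the plan says.** Objective 2 (section 3.2) is to describe clinical effectiveness through clinical parameters at days 1, 7 and 14. Section 4.10 (3) names the parameters (headache, fever, convulsion, abnormal mental status, death) but gives no rule for resolution or response. Under section 4.9 they are to be "described by number, percentage in treatment group". The shell for Table 8 is titled "Clinical effectiveness of study group by assessing presence of headache, fever, convulsion, abnormal mental status and death", with one N and one % per parameter at each of the three days, under a single treatment-group heading. The table prints no denominator and no rule for patients who have died by day 7 or 14.

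No individual symptom is required for entry (sections 4.6.1 and 4.10 (2)). Section 2.1.5 gives the frequencies to expect. In the African trial headache was near universal, "followed by fever (52.9%), abnormal mental status (46.7%) and seizure (19.2"%). In a Myanmar study of amphotericin B the figures after headache were "fever (58.70%), neck stiffness (45.65%) and impaired conscious level (13.04"%). A Myanmar study of fluconazole had abnormal mental status in 42.55% and convulsion in 41.3%.

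On size, section 4.7.1 concludes: "So, the required sample size is 27". Section 4.7.2 adds: "All patients admitted to the inpatient departments of SHW, SHM and SHT during the study period will be included". So 27 is a minimum, not a cap.

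**The concern.** The study has one group and no comparator (section 4.1), so change from day 1 is its only evidence on symptoms. A percentage of the whole group at each visit describes how common a symptom is on that day. It does not say what happened to the patients who had it. For headache the difference is small, because nearly everyone has it at entry. For convulsion and abnormal mental status, most of the denominator is expected to be free of the sign on day 1, so a later count mixes patients whose sign persisted with patients who newly developed it.

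Two things are at stake. First, a flat row may hide real resolution offset by new cases, and a falling row may reflect deaths among affected patients rather than recovery. Second, clinical safety in section 4.10 (4) is defined by laboratory events only. Table 8 is therefore the one place where a new convulsion or new mental-status change would appear, and there it is netted against resolution.

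**Working it through.** **1. The plan's own figure.** With n = z²p(1−p)/d² and z = 1.96 (section 4.7.1):
- effectiveness, p = 0.80, d = 0.15: 3.8416 × 0.16 / 0.0225 = 27.3
- safety, p = 0.83, d = 0.14: 3.8416 × 0.1411 / 0.0196 = 27.7

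Both agree with 27 to within one patient (strict rounding up gives 28). I use 27 below.

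**2. Expected patients with each sign on day 1.** 27 × the rate in section 2.1.5:

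| Sign | Source | Rate | 27 × rate | Expected without it |
|---|---|---|---|---|
| Convulsion | African trial | 19.2% | 5.2 | 21.8 (80.8%) |
| Convulsion | Myanmar fluconazole study | 41.3% | 11.2 | 15.8 (58.7%) |
| Abnormal mental status | Myanmar fluconazole study | 42.55% | 11.5 | 15.5 (57.5%) |
| Abnormal mental status | African trial | 46.7% | 12.6 | 14.4 (53.3%) |
| Impaired conscious level | Myanmar amphotericin B study | 13.04% | 3.5 | 23.5 (87.0%) |
| Fever | African trial | 52.9% | 14.3 | 12.7 (47.1%) |
| Fever | Myanmar fluconazole study | 85.11% | 23.0 | 4.0 (14.9%) |

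The impaired-consciousness rate is narrower than the protocol's definition of abnormal mental status in section 4.10. The two rates under the matching label give 11 to 13 patients; the narrower one gives about 4.

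The statement that more than half lack the sign is about expectation. If the counts are binomial with n = 27, the chance that 14 or more do have the sign is about 36% for mental status at 46.7%, and about 18% for convulsion at 41.3%.

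**3. What the row can and cannot identify.** Let a be the number with the sign on day 1. Of these, r have resolved and k have died by day 14. Let m be the number without the sign on day 1 who have it on day 14. If everyone alive is assessed, the day-14 count is

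a − r − k + m.

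Table 8 prints a and this total. It does not print r, k or m. With a = 5:

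| Course | Day 1 | Day 14 |
|---|---|---|
| Nobody changes | 5/27 (18.5%) | 5/27 (18.5%) |
| All 5 resolve, 5 of the other 22 are new | 5/27 (18.5%) | 5/27 (18.5%) |
| 4 resolve, none new, none die | 5/27 (18.5%) | 1/27 (3.7%) |
| 4 die, none resolve, none new | 5/27 (18.5%) | 1/27 (3.7%), or 1/23 (4.3%) of survivors |

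Four deaths is not an extreme figure: section 2.1.13 cites 14% mortality at two weeks in an earlier study, and 27 × 0.14 = 3.8. Placing all four among convulsing patients is an illustration, not a forecast.

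**4. Precision once the table is split.** Exact (Clopper-Pearson) 95% intervals for the proportion resolved, for outcomes near 80% (an assumed value, since the documents give no resolution rate for these signs):
- 4 of 5: 28% to 99%
- 9 of 11: 48% to 98%
- 10 of 13: 46% to 95%

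**The case against.** The study is descriptive and Table 8 does what Objective 2 asks: it describes the parameters on the three days. A reader might infer that the table cannot show any response to treatment. That goes too far. Day 1 stands beside days 7 and 14, so a fall from 5/27 to 1/27 is visible as a net change. A reader might also infer that the rows mostly count patients who never had the symptom. They do not: the rows count presence, and only the denominator is largely made up of patients without the sign. The rates are also rates at presentation, so they say nothing about ever having it.

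A third tempting reading is that section 4.7.1 promises 0.15 precision for every symptom, because its sub-heading reads "Sample size for clinical effectiveness". The text below that sub-heading defines p as improvement of headache, so the precision is already tied to headache. A wider interval for resolution among affected patients belongs to a different quantity and does not contradict the plan.

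It is also fair that no document gives a new-onset rate, so the amount of masking is unknown and exact cancellation is hypothetical. More than 27 patients may enrol, which would raise all the counts. The whole-group denominator is itself an inference, though a sound one, from section 4.9 and the table heading.

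What stands is structural. At any sample size, and for any symptom that not everyone has at entry, the printed row cannot separate resolution, new onset and death.

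**Conclusion.** The point holds as an inexpensive improvement to a stated objective; it does not invalidate the plan. Table 8 gives net change in prevalence and nothing within patients. At n = 27 this matters most for convulsion (about 5 to 11 affected on day 1) and abnormal mental status (about 11 to 13, or about 4 at the narrower rate). It matters less for fever (about 14 to 23) and little for headache.

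The counts assume that the section 2.1.5 rates carry over to these hospitals and that enrolment stops near the minimum. The inability to separate the components does not depend on either assumption. How far results would actually be distorted cannot be stated from the documents.

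**What to change.** In section 4.9 and Table 8, tabulate headache, fever, convulsion and abnormal mental status by day-1 status, at day 7 and at day 14:

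- **Sign present on day 1:** number and percentage resolved, persisting, died and not assessed. Use all day-1-positive patients as the denominator, so that a death is never counted as resolution, and give an exact 95% interval for the proportion resolved.
- **Sign absent on day 1:** number and percentage with new onset, died and not assessed.
- **Whole group:** keep the prevalence at each day, with its denominator stated.

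Add a sentence saying that the subset estimates will be imprecise, with an example such as 4 of 5 resolved (28% to 99%).

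The cost is table wording and simple cross-tabulation. Sections VI to IX of the pro forma (Annex 1) already record each symptom per patient on the three days. Section 4.8 has death reassessed at days 7 and 14, but the pro forma sections show no line for death or for not assessed, so one should be added if it is not recorded elsewhere. No extra patients, visits or tests are needed. The downside is that small denominators and wide intervals for convulsion and mental status become visible.
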